3 STUDY DESIGN

3.1 Overall Design

This is a Phase 3, open-label, single-arm, long-term safety study in which roflumilast cream 0.15% or roflumilast cream 0.05% is applied QD for 24 (Cohort-Week 24) or 52 (Cohort-Week 52) weeks to subjects with mild to moderate AD (except for time on BIW maintenance therapy).

Eligible subjects will enroll into the long-term safety study on the same day as the Week 4 visit of the preceding study (ARQ-151-311 or ARQ-151-312 or ARQ-151-315).

Subjects/caregivers will apply roflumilast cream 0.15% for subjects \geq 6 years old or roflumilast cream 0.05% for subjects 2-5 years old.

If a 5 year-old subject turns 6 years-old during this study, the subject will be switched from roflumilast cream 0.05% to roflumilast cream 0.15% at his/her first scheduled post-birthday visit. Dose reduction back to 0.05% is not permitted.

The study drug will be applied QD for 24 or 52 weeks (Cohort-Week 24 and Cohort-Week 52, respectively) to all AD affected areas and any newly appearing AD lesions that arise during the study, except on the scalp (unless entering BIW maintenance therapy, as described below).

For the first 4 weeks of study ARQ-151-313, all subjects will apply study medication QD in the areas identified and treated as per the body diagram in the preceding study (ARQ-151-311/312/315). Beginning at the Week 4 visit, any subject who achieves vIGA-AD of '0-clear' as confirmed by the Investigator at a scheduled or unscheduled clinic visit, will switch to BIW maintenance treatment. For maintenance therapy, study medication will be applied on two nonconsecutive days per week (e.g., Monday and Thursday) to areas commonly and/or most recently affected by AD, and any areas where AD is developing. Subjects receiving maintenance

[figure not shown]
Protocol Number: ARQ-151-313

Sponsor: Arcutis Biotherapeutics, Inc.

treatment who experience AD worsening (signs and symptoms) for 1 week despite dosing twice weekly will phone the clinical study site, resume daily dosing, and complete the subject diary accordingly. The phone call (but not a clinic visit) is required to resume daily dosing. At clinic visits, subjects receiving maintenance treatment may continue twice weekly maintenance dosing if vIGA-AD is either '0-clear' or '1-almost clear'. Subjects will resume daily dosing if vIGA-AD ≥ 2 and can resume daily dosing if signs/symptoms of AD are not adequately controlled with maintenance therapy despite vIGA-AD of '1-almost clear'.

Cohort-Week 24 was created under Amendment 1, to allow enrollment of additional subjects 6-17 years of age that have completed the 4-week treatment period in ARQ-151-311 or ARQ-151-312. Subjects in this cohort will receive treatment for 24 weeks with ARQ-151 cream 0.15% (Cohort-Week 24).

3.2 Study Schema

**STATISTICAL ANALYSIS PLAN, Final
Version 1.0**

Protocol Number: ARQ-151-313

Sponsor: Arcutis Biotherapeutics, Inc.

A Phase 3, Multicenter, Open-Label Extension Study of the Long-Term Safety of ARQ-151 Cream 0.15% and ARQ-151 Cream 0.05% in Subjects with Atopic Dermatitis

Up to approximately 1500 subjects that have completed the 4-week treatment period in studies ARQ-151-311 or ARQ-151-312 or ARQ-151-315 and are willing and qualified to enroll in this long-term extension study will receive ARQ-151 cream 0.15% (ARQ-151-311/312 roll-overs) or ARQ-151 cream 0.05% (ARQ-151-315 roll-overs).

** Under Amendment 1, 24 Week Treatment Period for Cohort-Week 24, Clinic Visits, and Phone Contact Weeks 4, 12, 18, 24

3.3 Schedule of Events

Table 1 Schedule of Visits and Assessments

Study Procedure	Day 1	Wk 4	Wk 12	Wk 18	Wk 24 ⁱ	Wk 30	Wk 36	Wk 44	Wk 52/ET
Visit #	1 (Week 4) of ARQ-151-311 or ARQ-151-312 or ARQ-151-315	2	3	Phone Visit	4	Phone Visit	5	Phone Visit	6
Visit Window	+/- 3 days	+/- 3 days	+/- 7 days	+/- 7 days	+/- 7 days	+/- 7 days	+/- 7 days	+/- 7 days	+/- 7 days
Informed consent/assent	X								
Physical examination ^a	X ^s	X				X			X
I/E criteria	X								
Hematology, Serum Chemistries, and Urine Analysis ^b	X ^s					X			X
Vital signs, height, weight ^c	X ^s	X	X			X			X
VIGA-AD, EASI, BSA, SCORAD ^d	X ^s	X	X			X			X
WI-NRS pruritus ^e	X ^s								
POEM ^f	X ^s	X	X			X			X
Local Tolerability Assessment ^g	X	X	X			X			X
CDI-2, PHQ-8, PHQ-A, C-SSRS ^h	X ^s	X	X			X			X
DLQI, CDLQI, IDQOL, DFI ⁱ	X ^s	X	X			X			X
Medical Photography ^j	X ^s	X	X			X			X
Urine pregnancy test ^k	X ^s	X	X			X			X
PK draws ^l						X			X
Dispense study medication kit ^m	X	X	X			X			X

Protocol Number: ARQ-151-313

Sponsor: Arcutis Biotherapeutics, Inc.

Study Procedure	Day 1	Wk 4	Wk 12	Wk 18	Wk 24 ^c	Wk 30	Wk 36	Wk 44	Wk 52/ET
Visit #	1 (Week 4) of ARQ-151-311 or ARQ-151-312 or ARQ-151-315	2	3	Phone Visit	4	Phone Visit	5	Phone Visit	6
Visit Window	+/- 3 days	+/- 7 days	+/- 7 days	+/- 7 days	+/- 7 days	+/- 7 days	+/- 7 days	+/- 7 days	+/- 7 days
Drug application and Parents/Caregivers training in clinic	X								
Dispense/review diary ^a	X	X	X		X		X		X
Maintenance Dosing Determination ^b		X	X		X		X		X
Weigh study medication ^b	X	X	X		X		X		X
Compliance Determination ^q		X	X		X		X		X
Adverse event assessment ^f	X	X	X	X	X	X	X	X	X
Concomitant medications	X	X	X	X	X	X	X	X	X
Study Exit					X ^t				X

^a Limited physical examination: skin, lungs, and heart only

^b Hematology, Serum Chemistrys, and Urine Analysis will only be done in subjects \geq 12 years of age at time of enrollment in the preceding study.

^c Height will be collected at Day 1 only for subjects \geq 18 years old and at every clinic visit for subjects $<$ 18 years old. Weight should be obtained using a calibrated weight scale and the same scale should be used for a subject throughout the duration of the study. The subject should remove shoes and heavy clothing (sweaters or jackets), and empty pockets. The subject should stand with both feet in the center of the scale with their arms at their side and hold still. Record the weight to the nearest decimal fraction (for example, 25.1 kilograms). For subjects $<$ 18 years of age, measure the weight in triplicate and report the average weight in EDC. A 5% or greater weight loss (whether or not intentional or otherwise explained) should be reported to the medical monitor.

^d The vIGA-AD assessment will be a 5-point scale ranging from clear (0) to severe (4) and is evaluated for the entire body except the scalp, palms, and soles. EASI takes into account overall severity of erythema, infiltration/papulation, excoriation, and lichenification, in addition to extent of BSA affected. The 4 clinical signs will be graded on a 4-point scale (0 [absent] to 3 [severe]) for 4 body regions (head and neck, upper extremities, lower extremities, and trunk). Total EASI score will be calculated as a sum of scores of all 4 body regions. EASI total score will range from 0 (absent) to 72 (severe). Total BSA affected by AD will be determined for all body surfaces except the scalp, palms and soles. vIGA-AD should be completed prior to other physician assessments. SCORAD total score will range between 0 and 103.

^e The WI-NRS pruritus questionnaire will be completed once a week at home utilizing a diary. **The WI-NRS will be self-reported by subjects for subjects \geq 6 years of age, and reported by parent/guardian for subjects $<$ 6 years of age.** During the Phone Visits at Weeks 18, 30, and 44 a reminder will be given to subjects to complete the WI-NRS pruritis questionnaire once a week.

^f POEM will be completed by all subjects either by self or by proxy completion (for children unable to read and/or understand the POEM questionnaire, the parent/guardian/caregiver will complete the questionnaire).

STATISTICAL ANALYSIS PLAN, Final Version 1.0

Protocol Number: ARQ-151-313

Sponsor: Arcutis Biotherapeutics, Inc.

^g At Day 1 only, local tolerability assessments should be recorded prior to study drug application for the investigator assessment of skin irritation (Berger and Bowman skin irritation score) and 10-15 minutes post-drug application for the Subject's '0-3' burning/stinging assessment. **Note for investigator tolerability assessments: reactions at the site of product application should be differentiated from the preexisting inflammation associated with the subject's atopic dermatitis. For subject tolerability assessments after Day 1, the subject will assess burning/stinging (0-3 score) 10-15 minutes post drug application based on recall of the last drug application.** For subjects <6 years of age, parents will complete.

^h Adolescents and adults (12 years and older) will complete the C-SSRS (12 years old of age and older). Adults will complete the PHQ-8. Adolescents (ages 12 to 17 years of age, inclusive) will complete the PHQ-A (PHQ-9 modified for Adolescents). Parents/caregivers will complete the parent report (CDI-2) for children 6-11 years of age, inclusive. Subjects will continue with the assessments specific to their age group at the time of consent/assent at Screening of the preceding study.

ⁱ The DLQI will be completed by subjects ≥17 years of age (based on age at start of preceding studies ARQ-151-311/312). The CDLQI will be completed for subjects ≥4 years of age and ≤16 years of age (based on age at start of preceding studies ARQ-151-311/312/315). The Infants' Dermatitis Quality of Life (IDQOL) will be completed by parents/caregivers for subjects <4 years (based on age at start of parent preceding studies ARQ-151-315). The Dermatitis Family Impact Questionnaire (DFI) will be completed by parents/caregivers for all subjects ≥ 2 years of age and ≤17 years of age. Subjects will continue with the assessments specific to their age group at the time of consent/assent at Screening of the preceding study. DFI is not to be conducted for subjects who were ≤17 years of age in the ARQ-151-311/312 studies and turned 18 years of age prior to enrollment into ARQ-151-313.

^j Photography will be performed using Canfield equipment on all subjects at all study sites. All efforts will be made to de-identify the subjects. Subjects who are unwilling to participate in the medical photography will be allowed to opt out of this procedure and documented on the informed consent. See Photography Manual for details.

^k A urine pregnancy test will be administered to all females of child-bearing potential. A negative result is required for continued participation in the study, and results must be available prior to dispensing of study drug at each visit.

^l For all subjects ≥12 years old entering this study under Amendment 1 a single PK trough draw will be collected at Week 52/ET for Cohort-Week 52 or Week 24/ET for Cohort 24 subjects. Ensure study medication was not applied in the area where PK will be drawn.

^m It is expected that kits will be dispensed based on %BSA affected and subject's age. Subjects who turn 6 years old during the study will switch to ARQ-151 cream 0.15% at their first scheduled post-birthday visit. See IP Handling Manual for details. Under Amendment 1, this is the final visit for Cohort-Week 24 and no kits will be dispensed at this visit.

ⁿ Dispensing of IP is allowed, if needed. Study site should review IP kit to ensure sufficient IP is available until the next visit and only dispense additional IP if needed. **All subjects will continue study medication application in the areas identified and treated as per the body diagram in the preceding study for the first 4 weeks of the current study (ARQ-151-313).**

^o Beginning at the Week 4 visit, any subject who achieves vIGA-AD of '0-clear' as confirmed by the Investigator at a scheduled or unscheduled clinic visit, will switch to twice weekly (BIW) maintenance treatment. For maintenance therapy, study medication will be applied on two nonconsecutive days per week (e.g. Monday and Thursday) to areas commonly and/or most recently affected by AD, and any areas where AD is developing. Subjects receiving maintenance treatment who experience AD worsening (signs and symptoms) for 1 week despite dosing twice weekly will phone the clinical study site, resume daily dosing, and complete the subject diary accordingly. The phone call (but not a clinic visit) is required to resume daily dosing. At clinic visits, subjects receiving maintenance treatment may continue twice weekly maintenance dosing if vIGA-AD is either '0-clear' or '1-almost clear'. Subjects will resume daily dosing if vIGA-AD ≥2, and can resume daily dosing if signs/symptoms of AD are not adequately controlled with maintenance therapy despite vIGA-AD of '1-almost clear'. Under Amendment 1, maintenance dosing determination will not be conducted at Week 24 for Cohort-Week 24.

STATISTICAL ANALYSIS PLAN, Final Version 1.0	
Protocol Number: ARQ-151-313	Sponsor: Arcutis Biotherapeutics, Inc.

^p The entire kit (every tube) should be weighed and recorded at every visit. See IP Handling Manual for details.

^q Compliance calculation is described in the IP Handling Manual

^r Any emergent AEs will be followed in the clinic for up to one month at the Investigator's discretion until resolved or otherwise judged as clinically stable.

^s This data will be obtained from Week 4 of ARQ-151-311/312/315 Study and used as the Day 1 data for this long-term safety study (ARQ-151-313).

^t Under Amendment 1, this is the final visit for Cohort-Week 24 from ARQ-151-311 and ARQ-151-312.

 Innovaderm Research	STATISTICAL ANALYSIS PLAN, Final Version 1.0
Protocol Number: ARQ-151-313	Sponsor: Arcutis Biotherapeutics, Inc.

3.4 Treatment

Initial treatment with the IP in the ARQ-151-313 will occur on Day 1 (Day 29 from the preceding study). Roflumilast cream 0.15% or roflumilast cream 0.05% is administered once daily (unless entering BIW maintenance therapy after Week 4) as a topical product to cover the skin surface at an application rate of approximately 2 mg/cm².

- Roflumilast cream 0.15%, QD (\geq 6 years old on Day 1 of ARQ-151-313)
- Roflumilast cream 0.05%, QD (2 -5 years old on Day 1 of ARQ-151-313)

Subjects who turn 6 years old during the study will switch to roflumilast cream 0.15% at their first scheduled post-birthday visit.

3.5 Randomization, and Unblinding Procedures

This is an open-label study, therefore the subjects, the Investigator, clinical personnel, and the sponsor will be aware of which treatment an individual subject receives; however, the treatment received during the prior study will remain blinded while the prior study is ongoing.

3.6 Changes to the Analysis from the Protocol

Rationale for change	Description of the change
A categorical summary of amount of investigational product used by each subject based on tube weights was excluded from the SAP as it was determined that it was not necessary.	
Original text:
 
The amount of investigational product used by each subject based on tube weight will be summarized by treatment using descriptive statistics, and categorically.
 
Changed to:
 
The amount of investigational product used by each subject based on tube weight will be summarized by treatment using descriptive statistics.

Analyses to be performed by cohorts (i.e., 24 vs. 52 weeks) were excluded from the SAP as it was determined that it was not necessary.	
Original text:
 
The analysis will be performed by cohorts and overall over time.
 
Changed to:

 Innovaderm Research	STATISTICAL ANALYSIS PLAN, Final Version 1.0
Protocol Number: ARQ-151-313	Sponsor: Arcutis Biotherapeutics, Inc.

Rationale for change	Description of the change
Update compliant criteria for subject who are on BIW dosing schedule.	
For analysis purposes, the TLFs will be summarized overall and by previous treatment group in the parent studies.
 
Subgroup analyses by Cohort will be performed for specific endpoints (refer to Section 6.6)

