I agree to maintain the confidentiality of all information received or developed in connection with this protocol.

Investigational Site Name: _____

Print Investigator Name: _____

Investigator Signature: _____ Date: _____

SUMMARY OF CHANGES

The following sections have been changed in Amendment 1 of the ARQ-151-313 protocol:

Version/Date	Description
December 20, 2020	Original Protocol
Amendment 1 September 17, 2021	
Added Summary of Changes section.Added statement that during the conduct of the study, additional countries and/or sites may be added if necessary.Sample size increased from approximately 400 to approximately 1500 subjects to allow:
All subjects from ARQ-151-315 to enroll into the ARQ-151-313 Open Label Extension study.An additional ~275 subjects ages 6-17 from ARQ-151-311 and additional ~275 subjects ages 6-17 from ARQ-151-312 to enroll into the ARQ-151-313 Open Label Extension study for a 24-week treatment period. This is Cohort-Week 24.Clarification added that if an unscheduled visit is required for reasons other than safety, the following assessments are not required:
vIGA-AD and EASIBSA affected with ADLocal tolerability assessment (by Investigator)Removed all safety labs for subjects ages 2-11; safety labs would have been evaluated at screening in the preceding study and the investigator may order safety labs at any time during the study to evaluate an adverse event.WI-NRS:
Added statement that caregiver/parents will be given instructions on how to complete this questionnaire for subjects between 2 and 5 years of age.Added that parent and/or guardian will be trained at the baseline visit to assist the subject, if needed, in the accurate completion of the WI-NRS for subjects \geq 6 years of age.Added clarification that only subjects 18 years and older will be enrolled at sites located in the province of Québec in Canada.

Version/Date	Description

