1. PROTOCOL SUMMARY

1.1. Synopsis

Name of Sponsor/Company: Acutis Biotherapeutics, Inc.		
Name of Investigational Product: ARQ-151 will be supplied as an emollient cream at 0.15% or 0.05% strength		
Name of Active Ingredient: Roflumilast, a PDE-4 inhibitor		
Protocol Number: ARQ-151-313	Phase: 3	Country: US and Canada
Title of Study: A Phase 3, Multicenter, Open-Label Extension Study of the Long-Term Safety of ARQ-151 Cream 0.15% and ARQ-151 Cream 0.05% in Subjects with Atopic Dermatitis		
Clinical Indication: Atopic Dermatitis		
Number of Sites: Up to approximately 120 study sites in the United States and Canada. During the conduct of the study, additional countries and/or sites may be added if necessary.		
Study Population: Up to approximately 1500 subjects that have completed the 4-week treatment period in studies ARQ-151-311 or ARQ-151-312 or ARQ-151-315 and are willing and qualified to enroll in this long-term extension study will receive ARQ-151 cream 0.15% (ARQ-151-311/312 roll-overs) or ARQ-151 cream 0.05% (ARQ-151-315 roll-overs) QD. Subjects 6-17 years of age enrolled under Amendment 1 will be treated for 24 weeks with ARQ-151 cream 0.15% (Cohort-Week 24). Subjects on ARQ-151 cream 0.05% who turn 6 years old during ARQ-151-313 will switch to ARQ-151 cream 0.15% at their first scheduled post-birthday visit.		
Objectives:		
Primary: To assess long-term safety in a multicenter, open-label, single-arm study in subjects with atopic dermatitis treated with ARQ-151 cream 0.15% QD (subjects \geq 6 years of age) or ARQ-151 cream 0.05% QD (subjects 2 to 5 years of age) after completing one of three Phase 3 studies (ARQ-151-311, ARQ-151-312, or ARQ-151-315).		

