6. DATA ANALYSIS

Data will be handled and processed according to the Contract Research Organization's Standard Operating Procedures, which are written based on the principles of GCP.

Full details of the statistical analysis will be included in the Statistical Analysis Plan (SAP).

Data from this study may be analyzed prior to the final analysis for regulatory reporting purposes. Under Amendment 1, subjects 6-17 years of age that have completed the 4-week treatment period in ARQ-151-311 or ARQ-151-312 will be treated for 24 weeks with ARQ-151 cream 0.15% (Cohort-Week 24). The rest of the subjects will be treated for up to 52 weeks with ARQ-151. The analysis will be performed by cohorts and overall over time.

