- Once the monotone pattern is achieved, the next step is to implement the imputation algorithm. For this, the PMM regression method will be used. This method is particularly helpful if the normality assumption is violated. For subjects with complete data up to a particular visit, a PMM regression model will be fit that includes the outcome at that visit as the dependent variable and as independent variables, the parent study randomized vIGA-AD stratification variable and parent study randomized treatment group, both as categorical variables, as well as the vIGA-AD score outcomes at previous analysis visits, all as continuous variables, using a seed of 482371. This process will be repeated 25 times, resulting in a total of 25 to 250 complete analysis datasets, depending on the number of

 Innovaderm Research	STATISTICAL ANALYSIS PLAN, Final Version 1.0
Protocol Number: ARQ-151-313	Sponsor: Arcutis Biotherapeutics, Inc.

imputed monotone datasets that are required. The seed may be changed after unblinding in case of any issues with the imputation process, and it will be documented in the CSR if any change is required.

3. For each multiply imputed dataset, Primary or OLE Baseline values, as applicable, will be derived as defined Section 5.2 and analysis visits from parent studies (OLE Week -4 to OLE Day 1) not selected as Primary or OLE Baseline, as applicable, will be dropped from each multiple imputed dataset.

For Cohort-Week 24 subjects, imputed OLE Week 36 and Week 52 analysis visit values will be set to missing given that these subjects will complete study at Week 24 or discontinue early from study before Week 24, whichever occurs first.

Finally, for each completed dataset, the vIGA-AD secondary efficacy endpoints will be derived by visit, as described in Section 12.2. Common proportion of success/achievement (and associated standard error [SE]) will then be calculated overall and by treatment group for each OLE analysis visit and combined using PROC MIANALYZE based on Rubin's rule to obtain a combined common proportion of success/achievement for each OLE analysis visit overall and treatment group. The combined common two-sided 95% CI will be calculated as per Lott and Reiter (2020)¹ multiple imputation Wilson interval method

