6.6 Examination of Subgroups

Subgroup analyses will be performed for the vIGA-AD secondary efficacy endpoints (refer to Section 12.2.3) as well as for the WI-NRS, EASI-50, and EASI-75 endpoints in the other efficacy endpoints (refer to Section 12.3.3) for the following subgroups relative to Primary Baseline only (refer to Section 5.2):

- Age group at informed consent in parent study (2 – 5 years, 6 – 11 years, 12 - 17 years, and \geq 18 years), including the WI-NRS endpoints. That is, although the main analysis for the WI-NRS endpoint in the other efficacy endpoints will be performed on subjects \geq 12 years old, a subgroup analysis will be performed for each of the previously defined age groups, including the 2 – 5 years and 6 – 11 years subgroups.
- Sex (Male and Female)
- Race (White, Black or African American, and Asian vs. Other)
- Ethnicity (Hispanic or Latino and Non-Hispanic or Latino)
- Actual Baseline vIGA-AD score (2- mild and 3- moderate) in parent study
- Prior inadequate response, intolerance, or contraindication to Topical Corticosteroids (yes and no)
- Facial Involvement (yes and no)

Subgroup analyses for rollovers from ARQ-151-311/312 will be performed for the duration, cumulative time, and percent of time other efficacy endpoints (refer to Section 12.3.3) for the following subgroups:

 Innovaderm Research	STATISTICAL ANALYSIS PLAN, Final Version 1.0
Protocol Number: ARQ-151-313	Sponsor: Arcutis Biotherapeutics, Inc.

- Cohort (Cohort-Week 24 and Cohort-Week 52)

Furthermore, to investigate long-term maintenance of the treatment effect, additional subgroup analyses will be conducted on subgroups below that are defined based on post-treatment characteristics. More specifically, subgroup analyses for rollovers from ARQ-151-311/312 will be performed for the BIW dosing and disease control other efficacy endpoints (refer to Section 12.3.3) for the following subgroups (by Cohort and overall):

- Subjects whose first interval started at OLE Week 4
- Subjects with vIGA-AD success at OLE baseline
- Subjects with vIGA-AD score of Clear (0) at OLE baseline

The subgroups criteria a and b as well as a and c will be combined for further subgroup analyses for the BIW dosing and disease control endpoints.

Additionally, the overall summary of treatment-emergent adverse events (TEAE) and summary of TEAEs by system organ class (SOC) and preferred term (PT) (refer to Section 13.1) will be presented by the age groups specified above.

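### Cohort columns are removed from the TEAE and by-visit efficacy tables, so the mixed-age 311/312 summaries blend 24- and 52-week follow-up and change population after Week 24

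*SAP*

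**What the plan says.** Protocol Section 6 states: "The analysis will be performed by cohorts and overall over time". SAP Section 3.6 quotes that sentence and replaces it with summaries overall and by parent-study treatment. It says that "Analyses to be performed by cohorts (i.e., 24 vs. 52 weeks) were excluded from the SAP", and the only reason given is that they were judged unnecessary. The same entry adds: "Subgroup analyses by Cohort will be performed for specific endpoints (refer to Section 6.6)". Section 6.6 then defines what survives: "Subgroup analyses for rollovers from ARQ-151-311/312 will be performed for the duration, cumulative time, and percent of time other efficacy endpoints". Section 7.1 also gives enrolled and treated counts by cohort.

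The cohorts differ in age and in length of follow-up. From the protocol synopsis: "Subjects 6-17 years of age enrolled under Amendment 1 will be treated for 24 weeks with ARQ-151 cream 0.15% (Cohort-Week 24)". From Protocol Section 6: "The rest of the subjects will be treated for up to 52 weeks with ARQ-151". The protocol's summary of changes sizes the shorter cohort: "An additional ~275 subjects ages 6-17 from ARQ-151-311 and additional ~275 subjects ages 6-17 from ARQ-151-312".

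SAP Section 5 tabulates 311/312 rollovers, who make up both cohorts, apart from 315 rollovers. Sections 5.6 and 13.1 report TEAEs as numbers and percentages of subjects, with EAIRs and 95% CIs beside them. For the main vIGA-AD analysis, Section 6.2.1 says of Cohort-Week 24 that "imputed OLE Week 36 and Week 52 analysis visit values will be set to missing". Section 12.2.1 summarizes EASI and WI-NRS on observed cases.

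**The concern.** Cohort-Week 24 is entirely aged 6-17 and leaves at Week 24 by design. Two things follow in any 311/312 summary that contains both cohorts.

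- **Safety.** A crude TEAE percentage is neither a 24-week nor a 52-week risk. Events that start late are diluted by subjects who were never followed long enough to have them, and long-term safety is the study's primary objective.
- **Efficacy over time.** Weeks 4 to 24 average the two cohorts, while Weeks 36 and 52 hold Cohort-Week 52 alone. An apparent gain or loss after Week 24 can come purely from who remains.

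The age subgroups do not separate the cohorts below 18. SAP Section 3.1 describes Cohort-Week 24 as additional 6-17-year-olds, which implies that earlier enrollees of that age are on 52 weeks. The interim analyses (Section 6.3) use only 311/312 rollovers, so they consist of the affected tables.

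**Working it through.** The plan has no figure of its own to reproduce. The sample size carries no formula and no hypothesis is tested, so what follows is illustration.

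**Inputs**
- Cohort-Week 24: 275 + 275 = 550 (protocol, summary of changes).
- Cohort-Week 52 among 311/312 rollovers: not stated. I assume 400, borrowed from the total sample size before Amendment 1, with a range of 200 to 600.
- Exposure: 24 × 7 = 168 days and 52 × 7 = 364 days, no dropout.
- EAIR (SAP Section 5.5): subjects with an event ÷ total exposure days × 365.25 × 100.
- All event and response rates are assumed.

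**Mix.** 550/950 = 57.9% of the 311/312 column has 24-week follow-up (73.3% with 200 in Cohort-Week 52, 47.8% with 600). Total exposure is 550 × 168 + 400 × 364 = 238,000 days.

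**TEAEs**

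*Constant hazard, 52-week risk 10%.* The 24-week risk is 1 − 0.9^(24/52) = 4.75%. Pooled crude: (550 × 0.0475 + 400 × 0.10)/950 = 7.0%.

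*Late event, 5% in Cohort-Week 52, all after Week 24.* 400 × 0.05 = 20 subjects. Pooled crude: 20/950 = 2.1%. Pooled EAIR: 20/238,000 × 36,525 = 3.1. Cohort-Week 52 EAIR: 0.05/364 × 36,525 = 5.0.

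*Early event, 5% in both cohorts in the first weeks.* The crude figure is right at 5%. Pooled EAIR: 47.5/238,000 × 36,525 = 7.3.

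| Pattern | Crude: Wk 24 / Wk 52 / pooled | EAIR: Wk 24 / Wk 52 / pooled |
|---|---|---|
| Constant hazard | 4.7% / 10.0% / 7.0% | 10.3 / 10.0 / 10.1 |
| Late onset | 0 / 5.0% / 2.1% | 0 / 5.0 / 3.1 |
| Early onset | 5.0% / 5.0% / 5.0% | 10.9 / 5.0 / 7.3 |

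For the late event, the pooled figures run from 1.3% and 2.2 (200 in Cohort-Week 52) to 2.6% and 3.5 (600).

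**By-visit efficacy.** Let response be flat within each cohort. The pooled Week 24 value is (550 × p24 + 400 × p52)/950 and the Week 36 value is p52, so the step is (550/950) × (p52 − p24). With 45% and 55%, the curve goes from 49.2% to 55.0%, a step of 5.8 points. Reversed, it goes from 50.8% to 45.0%. For the same 10-point difference the step is 7.3 points with 200 in Cohort-Week 52 and 4.8 with 600. These shares fit vIGA-AD and EASI. The main WI-NRS analysis is limited to age 12 and over, where the documents do not give the cohort split; the mechanism is the same but the size is unknown.

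**Denominators at Weeks 36 and 52.** The exception for Cohort-Week 24 is written for multiple imputation only. Section 6.2.2 (non-responder imputation) has none, and the default denominator in Appendix 1 is everyone in the population per treatment group. Read literally, a 50% Week 52 response among 400 would show as 200/950 = 21%.

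**The case against.** The strongest reply is that the plan already adjusts for exposure. With a 40% 52-week risk at constant hazard, the crude contrast looks stark: 21%, 40% and 29% pooled. The EAIRs in the same tables would be about 45.7, 40.1 and 42.3 per 100 subject-years. A reader might infer that the TEAE tables have no remedy for unequal follow-up. They do, and it works well for this pattern. It fails when the hazard changes over time, and it does nothing for efficacy.

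A reader might also infer that cohort analysis is gone altogether. It is not. Section 6.6 keeps it for all duration and time endpoints, including time with vIGA-AD 0 and with 0 or 1, and disposition is split too. Nor is this a concealed departure: Section 3.6 prints the old and new text.

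Nor is every summary affected. The 315 tables contain only 52-week subjects. So does the 18-and-over group, which gets its own TEAE tables (Section 13.1) and vIGA-AD time course (Section 6.6). That relief is incomplete, because change in EASI has no age-group analysis under Sections 12.2.3 and 12.3.3.

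Finally, the table in Section 6.2.1 marks Weeks 36 and 52 as Cohort-Week 52 only, so the change of population is visible to a careful reader. This also suggests that the missing non-responder exception is an omission rather than an intention. Visibility does not remove the step.

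**Conclusion.** The point holds for the all-ages 311/312 summaries and for those aged 6-17. Crude TEAE percentages there mix two lengths of follow-up, and the EAIRs correct this only when the hazard is roughly constant. By-visit vIGA-AD, EASI and WI-NRS change population between Weeks 24 and 36.

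Assuming 550 and 400 subjects, a late 5% event is understated by more than half in crude terms (2.1%) and by about two fifths as an EAIR (3.1 against 5.0). A 10-point cohort difference in response produces a spurious 5.8-point step. The 400, the event rates and the 10-point difference are assumptions; the step scales directly with the last and vanishes if the cohorts respond alike.

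The stronger conclusion, that the study cannot give a long-term safety answer, is not supported: EAIRs, the adult tables and the 315 tables all remain. This is a thinly justified presentation choice in a descriptive study, and correcting it is a cheap improvement.

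**What to change.** 1. Add cohort columns to the 311/312 TEAE overview, the TEAE tables by SOC and PT, and the by-visit tables of the secondary efficacy endpoints. Keep the pooled column.
2. Show the long-term time course for Cohort-Week 52 across all visits, Day 1 to Week 52. Restricting only the visits after Week 24 would leave the step in place, because the earlier points would still average both cohorts.
3. State in SAP Sections 6.2.2 and 12.2 and in Appendix 1 that Week 36 and Week 52 denominators, including those under non-responder imputation, contain Cohort-Week 52 only.

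This was the protocol's own plan and needs no new data. Cohort is already used in the disposition and time-endpoint outputs. The cost is more table pages and smaller counts per column, hence wider intervals for the EAIRs and response proportions within each cohort.
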